7.6.4 Adverse Events Leading to Dose Modification

AEs leading to dose delay/reduction will be summarized by treatment group:

- Overall summary of AEs leading to dose delay/reduction by worst CTC grade (any grade, grade 3-4, grade 5) presented by SOC/PT
- Overall summary of related AEs leading to dose delay/reduction by worst CTC grade (any grade, grade 3-4, grade 5) presented by SOC/PT

The analysis will be conducted using the 30-day safety window.

A by-subject AEs leading to dose delay/reduction listing will be provided.

7.6.5 Adverse Events

Adverse events will be summarized by treatment group.

The following analyses will be conducted using the 30 days safety window only:

- Overall summary of any AEs by worst CTC grade (1, 2, 3, 4, 5, not reported, total) presented by SOC/PT. This analysis will be performed on the All Treated LAG-3 Positive Subjects, All Treated LAG-3 Negative Subjects, and All Treated Subjects, and All Treated Subjects by Chemotherapy
- Overall summary of any AEs presented by worst CTC grade (any grade, grade 3-4, grade 5) by SOC/PT. This table will be restricted to events with an incidence greater or equal to 5% in any treatment group.
- Overall summary of any non-serious AEs presented by SOC/PT. This table will be restricted to events with an incidence greater or equal to 5% in any treatment group
- Overall summary of any AEs that required immune modulating medication by worst CTC grade (any grade, grade 3-4, grade 5) presented by SOC/PT
- Overall summary of drug-related AEs by worst CTC grade (1, 2, 3, 4, 5, not reported, total) presented by SOC/PT. This analysis will be performed on the All Treated LAG-3 Positive Subjects, All Treated LAG-3 Negative Subjects, and All Treated Subjects.

The following analyses will be conducted using the 30 days safety window and repeated using the 100 days safety window:

- Overall summary of drug-related AEs by worst CTC grade (any grade, grade 3-4, grade 5) presented by SOC/PT

A by-subject AE listing will be provided. A by-subject listing of any AE requiring immune modulating medications will also be provided.

7.6.6 Select Adverse Events (EU/ROW Submissions)

Unless otherwise specified, analyses will be performed by select AE category. Analyses will also be repeated by subcategory of endocrine events.

7.6.6.1 Incidence of Select AE

Select AEs will be summarized by treatment group for each category/subcategory.

The following analyses will be conducted using the 30-day safety window only:

- Overall summaries of any select AEs by worst CTC grade (any grade, grade 3-4, grade 5) presented by Category or Subcategory/PT
- Overall summaries of any drug-related select AEs by worst CTC grade (any grade, grade 3-4, grade 5) presented by Category or Subcategory/PT
- Overall summaries of any serious select AEs by worst CTC grade (any grade, grade 3-4, grade 5) presented by Category or Subcategory /PT
- Overall summaries of drug-related serious select AEs by worst CTC grade (any grade, grade 3-4, grade 5) presented by Category or Subcategory /PT
- Overall summaries of any select AEs leading to discontinuation by worst CTC grade (any grade, grade 3-4, grade 5) presented by Category or Subcategory /PT
- Overall summaries of drug-related select AEs leading to discontinuation by worst CTC grade (any grade, grade 3-4, grade 5) presented by Category or Subcategory /PT
- Summary of frequency of unique select AEs by Category

A by-subject select AE listing will be provided.

7.6.6.2 Time-to Onset of Select AE

Time-to onset of drug-related select AEs (any grade, grade 3-5) will be summarized for each category/subcategory by treatment group.

Time-to onset analyses are restricted to treated subjects who experienced at least one drug-related select AE in the category/subcategory. The analyses will be conducted using the 30-day safety window.

Additional details regarding the time-to onset definition are described in time-to onset definition subsection of [APPENDIX 1](#).

7.6.6.3 Time-to Resolution of Select AE

Time-to resolution of the following specific events will be summarized separately for each category/subcategory.

- Time-to resolution of drug-related select AE (any grade, grade 3-5) by treatment group
- Time-to resolution of drug-related select AE (any grade, grade 3-5) where immune modulating medication was initiated, by treatment group

Time-to resolution analyses are restricted to treated subjects who experienced the specific events. Time-to resolution where immune modulating medication was initiated analyses are restricted to treated subjects who experienced the specific events and who received immune modulating medication during the longest select AE.

The analyses will be conducted using the 30-day safety window.

The following summary statistics will be reported: percentage of subjects with resolution of the longest select AE, median time-to resolution along with 95% CI (derived from Kaplan-Meier estimation) and ranges.

See time-to resolution definition subsection of [APPENDIX 1](#) for additional details.

7.6.7 Immune-Mediated Adverse Events (US Submission)

IMAEs will be summarized by treatment group for each immune-mediated category / PT using the 100-day safety window:

- Overall summary of non-endocrine IMAEs by worst CTC grade (any grade, grade 3-4, grade 5) where immune modulating medication was initiated presented by Category / PT
- Overall summary of endocrine IMAEs by worst CTC grade (any grade, grade 3-4, grade 5) presented by Category / PT
- Overall summary of non-endocrine IMAEs leading to discontinuation by worst CTC grade (any grade, grade 3-4, grade 5) where immune modulating medication was initiated presented by Category / PT
- Overall summary of endocrine IMAEs leading to discontinuation by worst CTC grade (any grade, grade 3-4, grade 5) presented by Category / PT
- Overall summary of non-endocrine IMAEs leading to dose delay or reduction by worst CTC grade (any grade, grade 3-4, grade 5) where immune modulating medication was initiated presented by Category / PT
- Overall summary of endocrine IMAEs leading to dose delay or reduction by worst CTC grade (any grade, grade 3-4, grade 5) presented by Category / PT
- Summaries of time-to onset and time-to resolution of non-endocrine IMAEs where immune modulating medication was initiated presented by Category
- Summaries of time-to onset and time-to resolution of endocrine IMAEs presented by Category

A by-subject listing of IMAEs will be provided. By-subject listings of time-to resolution for longest IMAEs cluster (any grade and grade 3-5 in separate summaries) will also be provided. For new studies which collect investigator assessment of potential IMAE data, a by-subject listing of AEs considered as immune-mediated events per investigator but not qualified for IMAEs definition will also be provided.

7.6.8 Other Events of Special Interest

OEOSI will be summarized by treatment group for each category.

The following analyses will be conducted using the 100-day safety window:

- Overall summary of OEOSI by worst CTC grade (any grade, grade 3-4, grade 5) presented by Category / PT
- Overall summary of drug-related OEOSI by worst CTC grade (any grade, grade 3-4, grade 5) presented by Category / PT

A by-subject listing of OEOSI will be provided.

7.6.9 Multiple Events

The following summary tables will be provided:

- A table showing the total number and rate (exposure adjusted) of occurrences for all AEs

- A table showing the total number and rate (exposure adjusted) of occurrences for AEs occurring in at least 5% of subjects in any treatment group

A listing displaying the unique instances of all AEs, i.e., after duplicates have been eliminated and overlapping and contiguous occurrences of the same event (i.e. same PT) have been collapsed will be provided. No formal comparisons will be made between treatment groups.

7.6.10 Laboratory Parameters

The analysis population for each laboratory test is restricted to treated subjects who underwent that laboratory test.

7.6.10.1 Hematology

The following will be summarized by treatment group as worst CTC grade on-treatment per subject and as shift table of worst on-treatment CTC grade compared to baseline CTC grade per subject: hemoglobin (HB), platelets, white blood counts (WBC), absolute neutrophils count (ANC) and lymphocyte count (LYMPH).

The analyses will be conducted using the 30-day safety window.

A by-subject listing of these laboratory parameters will be provided.

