FOLFOX	X	See Note	First dose to be administered within 72 hours after randomization. FOLFOX dose schedule: see Table 7.1.3-1 . Subsequent FOLFOX doses may be administered within dosing windows per package insert or local standard.

Abbreviations: BP = blood pressure; C = cycle; D = day; ECG = electrocardiogram; ECOG = Eastern Cooperative Oncology Group; [REDACTED]
[REDACTED] FOLFOX = oxaliplatin, leucovorin, and fluorouracil; FU = Follow-up; HCG = human chorionic gonadotropin; IV = intravenous; NCI CTCAE = National Cancer Institute Common Terminology Criteria for Adverse Events; MRI = magnetic resonance imaging; [REDACTED]
[REDACTED] SAE = serious adverse event; concentration; [REDACTED] WOCBP = women of childbearing potential

^a If a dose is delayed, the procedures scheduled for that same time point should also be delayed to coincide with when that time point’s dosing actually occurs, except for body imaging, [REDACTED] and pregnancy testing.

Table 2-4: Follow-up Assessments - All Participants (CA224060)

Procedure	Follow-Up ^a Visits 1 and 2	Survival Follow-Up Visits ^b	Notes
Safety Assessments			
Targeted Physical Examination	X		Weight, BP, HR, and temperature. Targeted physical examination to be performed only as clinically indicated.
Serious Adverse Events Assessments	X		Assessed using NCI CTCAE v5
Adverse Events Assessment	X		Assessed using NCI CTCAE v5
Review of Subsequent Cancer Therapy	X	X	
Laboratory Tests	See Note		For Follow-up Visit 1, including Hematology, Serum Chemistry, and Urinalysis as outlined in Table 9.4.4-1 . Repeat at Follow-up Visit 2 if study treatment related toxicity persists.
Pregnancy Test (WOCBP only)	See Note		Serum or urine pregnancy testing is only required at FU1 and FU2 visits, unless increased frequency and duration is required per local regulations.

Table 2-4: Follow-up Assessments - All Participants (CA224060)

Procedure	Follow-Up ^a Visits 1 and 2	Survival Follow-Up Visits ^b	Notes
Efficacy Assessments			
Body imaging	See Note	See Note	See Section 9.1.1. For participants who discontinue study drug for reasons other than PD, follow-up scans should be performed every 6 weeks (± 7 days) up to and including Week 48, then every 12 weeks (± 7 days) until BICR confirmed PD, lost to follow-up, or withdrawal of consent. Radiographic assessments should be Q12W in Follow-Up and not be delayed until follow-up visits 1 & 2.

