Brain Imaging	See Note	See Note	See Section 9.1.1. Participants with a history of brain metastasis or symptoms should have surveillance MRI per standard of care (approximately every 12 weeks), or sooner if clinically indicated

Abbreviations:

Adverse Events; FU = Follow-up; NCI CTCAE = National Cancer Institute Common Terminology Criteria for Adverse Events; WOCBP = women of childbearing potential

^a Follow-up visits occur as follows: Follow-up Visit 1 = 30 days from the last dose (± 7 days) or coincide with the date of discontinuation (± 7 days) if date of discontinuation is greater than 42 days after last dose. Follow-up Visit 2 = 100 days (± 7 days) from last dose of study treatment. Participants must be followed for at least 100 days after last dose of study treatment. Both Follow-up visits should be conducted in person.

^b Survival follow-up visits may be conducted in clinic or by phone. The first survival follow-up visit will occur 3 months (± 14 Days) after Follow-up Visit 2, subsequent survival follow-up visits will occur every 3 months (± 14 days) thereafter. BMS may request that survival data be collected on all treated participants outside of the 3 month specified window. At the time of this request, each participant will be contacted to determine their survival status unless the participant has withdrawn consent for all contacts.

[figure not shown]

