5.1.3 Follow-up Phase

- The Follow-up Phase begins when the decision is made to discontinue a participant from study therapy.
- Follow-up Visit 1 will be performed 30 days from the last dose (± 7 days) or coincide with the date of discontinuation (± 7 days) if date of discontinuation is greater than 42 days after last dose. Follow-up Visit 2 will be performed 100 days (± 7 days) from last dose of study treatment. Participants must be followed for at least 100 days after last dose of study treatment. Both follow-up visits should be conducted in person.
- Survival visits - The first survival follow-up visit will be performed 3 months (± 14 days) after follow-up Visit 2. Subsequent survival follow-up visits will occur every 3 months (± 14 days) thereafter. Survival follow-up visits may be conducted in clinic or by phone.

Study follow-up assessment data are to be collected as outlined in [Table 2-4](#).

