10.3.3 Safety Analyses

All safety analyses will be performed on the Safety Sample.

Endpoint	Statistical Analysis Methods

Secondary
 
The Safety and tolerability objective will be measured by the incidence of adverse events (AEs), serious adverse events (SAEs), adverse events leading to discontinuation, deaths, and laboratory abnormalities in each arm by LAG-3 group and overall	
Safety analyses will be performed in all treated participants. Descriptive statistics of safety will be presented using National Cancer Institute (NCI) Common Terminology Criteria for Adverse Events (CTCAE) version 5.0 by treatment group. All on-study AEs, treatment-related AEs, SAEs, and treatment-related SAEs will be tabulated using worst grade per NCI CTCAE v 5.0 criteria by system organ class and preferred term. On-study lab parameters including hematology, chemistry, liver function, and renal function will be summarized using worst grade NCI CTCAE v 5.0 criteria.

[figure not shown]

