- ◆ For PD-L1, among the records prior to or on first dose date (and time if collected), identify first those with quantifiable test result. If there are no records with quantifiable test result, then select those with indeterminate result (“INDETERMINATE”). If there are no records with indeterminate test result, then select those with unavailable result (“NOT EVALUABLE”). If there are no records with unavailable test result, then select those with not reported or not available result (all other records). The latest record will be used as the baseline in the analyses. If there is more than one record for the latest date, then choose the one with the greatest specimen ID.

- Post baseline period:
 - On-treatment AEs will be defined as AEs with an onset date and time on or after the date and time of the first dose of study treatment (or with an onset date on or after the day of first dose of study treatment if time is not collected or is missing). For subjects who are off study treatment, AEs will be included if event occurred within a safety window of 30 days (or 100 days depending on the analysis) after the last dose of study treatment. No “subtracting rule” will be applied when an AE occurs both pre-treatment and post-treatment with the same preferred term and grade.
 - On-treatment evaluations (laboratory tests and vital signs) will be defined as evaluations taken after the day (and time, if collected and not missing) of first dose of study treatment. For subjects who are off study treatment, evaluations should be within a safety window of 30 days (or 100 days depending on the analysis) after the last dose of study treatment.
- Late-emergent drug-related AEs will be defined as drug-related AEs with an onset date greater than 100 days after the last dose of study treatment in subjects who are off study treatment.

- In addition, data collected within an extended follow-up window of 135 days based on specific EU country requests, will be presented in listings.

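### The SAP's laboratory tables stop at day 30 after last dose, the midpoint of the window for the only routine post-treatment draw, so scheduled values are tabulated or left out according to the visit day

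*SAP*

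**What the plan says.** SAP 6.1 defines which values count once a subject is off treatment: laboratory "evaluations should be within a safety window of 30 days (or 100 days depending on the analysis) after the last dose of study treatment". SAP 7.6.10.1 to 7.6.10.4 then choose 30 days for every laboratory table. The hematology section reads "The analyses will be conducted using the 30-day safety window", and the chemistry, electrolyte, hepatic and thyroid sections say the same. None asks for a 100-day repeat.

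Protocol Table 2-4 schedules laboratory tests "For Follow-up Visit 1, including Hematology, Serum Chemistry, and Urinalysis as outlined in" Table 9.4.4-1, and then adds: "Repeat at Follow-up Visit 2 if study treatment related toxicity persists". So Visit 1 is the only post-treatment visit with an unconditional draw. Under Protocol 5.1.3 (restated in SAP 2.1), Visit 1 takes place 30 days after last dose, plus or minus 7 days. It moves to the discontinuation date, plus or minus 7 days, "if date of discontinuation is greater than 42 days after last dose". For the later visit, "Follow-up Visit 2 will be performed 100 days (± 7 days) from last dose of study treatment".

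Protocol 10.3.3 sets no day limit: "On-study lab parameters including hematology, chemistry, liver function, and renal function will be summarized using worst grade NCI CTCAE v 5.0 criteria".

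**The concern.** The analysis cutoff sits on the nominal day of the visit whose results it should capture. Two participants with the same abnormality at an on-schedule Visit 1, one seen on day 29 and the other on day 32, are treated differently: the first enters the worst-grade and shift tables and the second does not. I found no SAP rule that assigns an in-window Visit 1 draw to the 30-day period.

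Laboratory abnormalities are a named component of the secondary safety endpoint (Protocol Table 4-1, SAP Table 3-1). What is at stake is whether the tabulated incidences reflect the safety data that the protocol schedules. The SAP also uses 100 days for immune-mediated hepatitis and thyroid events (7.1.1.3, 7.6.7), but only 30 days for the matching hepatic and thyroid laboratory tables (7.6.10.4).

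There is a related point in SAP 7.6.3. SAP 7.1.1 identifies AEs leading to discontinuation by the recorded action alone, yet 7.6.3 tabulates them within 30 days of last dose.

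**Working it through.** The plan gives no figure to reproduce. The check compares the permitted visit days with the analysis cutoff, counting days after the last dose.

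**Inputs.** The cutoff is day 30 (SAP 7.6.10.1 to 7.6.10.4). Standard Visit 1 is 30 ± 7, and late-branch Visit 1 is D ± 7 with discontinuation day D of at least 43 (Protocol 5.1.3 and Table 2-4, footnote a). Visit 2 is 100 ± 7 (same places).

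**Permitted days lost at each cutoff.**

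| Visit | Permitted days | Lost at day 30 | Lost at day 37 | Lost at day 100 |
|---|---|---|---|---|
| Visit 1, standard | 23–37 | 7 of 15 | 0 | 0 |
| Visit 1, D = 43 | 36–50 | 15 of 15 | 13 of 15 | 0 |
| Visit 1, D = 100 | 93–107 | 15 of 15 | 15 of 15 | 7 of 15 |
| Visit 1, D = 108 | 101–115 | 15 of 15 | 15 of 15 | 15 of 15 |
| Visit 2 | 93–107 | 15 of 15 | 15 of 15 | 7 of 15 |

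- Standard Visit 1: the window has 37 − 23 + 1 = 15 days, of which 37 − 30 = 7 are late, and 7/15 = 46.7%.
- Late branch: the earliest visit is 43 − 7 = day 36, so every permitted day is past day 30.
- A 100-day cutoff loses nothing in the late branch up to D = 93, because 93 + 7 = 100.

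**Share of draws lost.** The 46.7% is a share of permitted calendar days. The share of actual draws depends on visit timing, which the documents do not give. Under stated assumptions:

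- Visits spread evenly over days 23–37, no late branch: 46.7%.
- Visits normally distributed, truncated to days 23–37, mean 28 to 32 and SD 2 to 4 days: about 11% (mean 28, SD 2) to 77% (mean 32, SD 2).
- Even spread with 10% of participants in the late branch: 0.10 + 0.90 × 7/15 = 52%. With 30%: 0.30 + 0.70 × 7/15 = 63%.

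**AEs leading to discontinuation.** For an AE to be missed by 7.6.3, its onset must be more than 30 days after the last dose of any study drug. Protocol Section 7 counts chemotherapy as study treatment, and SAP Tables 7.4.1-1 to 7.4.1-3 end treatment duration at the last dose of the last administered therapy. The same event, if it qualifies as immune-mediated, would be counted under 7.6.7, which uses 100 days for immune-mediated AEs leading to discontinuation.

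**The case against.** The case for leaving the plan alone is substantial. SAP 6.1 expressly allows 30 or 100 days by analysis and the protocol sets no limit, so nothing is contradicted. Day 30, the nominal visit day, is inside the window. By-subject laboratory listings are provided with no stated 30-day limit. Protocol 9.2.6 requires clinically significant values, and those causing interruption, discontinuation or corrective therapy, to be recorded as AEs. SAP 7.6.5 repeats the drug-related AE table at 100 days. The tables take one worst grade per subject, so an abnormality that prompted a hold is normally already counted, and Visit 2 repeats concern toxicity that arose earlier. Safety comparisons carry no p-values.

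All of this limits the size of the problem. It does not restore the tabulated incidence of an abnormality that first appears, or reaches its worst grade, at a Visit 1 held on day 31 or later.

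Several stronger readings are tempting, and the documents do not support them:

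- *Nearly half of Visit 1 laboratory data is lost.* The 7 of 15 counts days, not draws.
- *Participants held longest lose their laboratory data entirely.* They lose only later values, and only from the tables. Held participants are re-evaluated at least weekly (Protocol 7.3.5), values to day 30 count, and the cutoff applies only once a subject is off treatment.
- *The cutoff favours the arm with more holds.* No hold rates by arm are given, so neither direction nor size can be derived.
- *The delay limits in Protocol 7.3.7 leave days 31–42 (Q3W) or 31–56 (Q4W) uncounted for discontinuation AEs.* Those limits run from the previous immunotherapy dose, while the SAP's 30 days run from the last dose of study treatment. A completed 14-day oral course ends 13 days after the infusion, and 42 − 13 = 29, which is inside the window. With the FOLFOX Day 15–16 treatment given, 56 − 15 = 41. Protocol 7.3.7 also allows longer delays for steroid tapers, so 42 and 56 are not upper limits either.
- *Any hold past day 30 removes the AE that ends treatment.* An AE that causes the hold usually starts earlier and is counted. The missed case needs a new onset after more than 30 days off all study drugs.

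**Conclusion.** The point holds as a design weakness in the safety tables. The 30-day cutoff leaves 7 of 15 permitted standard Visit 1 days, every late-branch Visit 1 draw and every Visit 2 repeat out of the worst-grade, shift, hepatic and thyroid tables. The thyroid table is affected only where TSH is drawn at follow-up, since Table 9.4.4-1 labels TSH as screening and on treatment. These counts rest on the visit windows as written and on applying SAP 6.1 literally.

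A 30-day window is not wrong in itself. The weakness is its placement at the midpoint of the scheduled visit window, without a longer-window repeat. The number of values lost and any effect on the comparison between arms cannot be established from the documents.

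The 7.6.3 point is secondary and probably concerns few events. SAP 7.1.1 does restrict AE tables to on-treatment events unless otherwise specified, so the cutoff follows a general rule. It still narrows the action-based definition in the same section and differs from the 100-day window in 7.6.7. The gap is partly covered by the 7.6.3 listing and by the table of discontinuation reasons in 7.3.1, which has no day limit.

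**What to change.** In SAP 7.6.10, keep the 30-day tables and add a repeat using the 100-day window from SAP 6.1. State that any protocol-scheduled Follow-up Visit 1 or Visit 2 draw is included in the repeat whatever its exact day. Without that rule, a 100-day cutoff would split the Visit 2 window (7 of 15 days lost) and miss some Visit 1 draws when D is 94 or later. A 37-day window is not enough, because it misses almost all late-branch draws. Flag values taken after the start of subsequent therapy.

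In SAP 7.6.3, count every AE with the action *Drug was discontinued*, whatever the time since last dose, as defined in 7.1.1.

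The cost is SAP wording, one additional set of tables, and a date-window and visit rule in programming, with no new data collection. Reported incidences may rise slightly, and some late values may reflect subsequent therapy rather than study treatment. The flag and the retained 30-day tables let readers judge that.
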